#### 4.1.4 Drug assignment and administration of doses for each patient

Patients in Study Cohort will be treated with BI 655130 as indicated in the [Flow Chart](#) and [section 3.1](#).

The medication will be assigned via IRT for period 1 and 2.

Detailed instructions for the preparation of the solution for infusion, the volume to be administered and the infusion rate (BI 655130 i.v.) are provided in the ISF.

The administration of the trial medication on all applicable study days will be done under supervision of the investigating physician or a designee at the site. If available, a pharmacist should prepare the study medication. The so-called four eye principle (two-person rule) should be applied for preparation (e.g. choosing the correct vials with the correct medication number) and administration of trial medication.

During the COVID-19 pandemic, physical visits to the sites may need to be restricted to ensure patient safety. Based on a thorough assessment of the benefits and risks, the investigator may discuss with BI to continue the trial treatment and trial medication may be shipped to the patient's home if acceptable according to local law and regulations.

In case of safety concerns, e.g., due to infusion reactions, it is in the discretion of the investigator or his/her designee to adapt the infusion scheme, including but not limited to slowing down the infusion rate, interrupting the infusion and - provided no further safety concern exist - restarting at a slower rate. Further, based on [REDACTED] medical judgment he/she will provide medications such as steroids, etc., as needed (cf. [section 4.2.1](#) for handling of infusion reactions). Detailed instructions for handling of infusion reactions are also provided in the ISF.

Dose modifications or adjustments are not permitted. In exceptional cases of missed or delayed visits, study drug of the following visit should not be administered within 14 days of the prior dose. There should be at least 14 days between two consecutive study drug administrations.

#### 4.1.5 Blinding and procedures for unblinding

##### 4.1.5.1 Blinding

###### Study Cohort, Period 1 and 2: Double blind

Patients and investigators (including the research staff at the trial site) will remain blinded with regard to the randomized treatment assignments until the final database lock for the final trial analysis.

The interim analysis, which is the primary analysis of the trial will be performed once all randomized patients have completed through 12 weeks of trial treatment. At this time, a preliminary database lock will be done and treatment will be unblinded. In order to confirm the integrity of the treatment blind while the trial continues through to completion, a logistics plan will be developed to describe the mechanisms that are to be put in place to assure that

the patients and investigators remain blinded to both individual patient data, as well to the primary analysis results. The blind status of trial and project team members at this time will also be clarified. The logistics plan will be finalized prior to the treatment unblind for the primary analysis.

The randomization code will be kept secret by Clinical Trial Support and will not be accessible prior to the preliminary database lock for the interim analysis by anyone else involved in the trial with two exceptions. The bioanalytical laboratory will receive the randomization code during the trial conduct in order to avoid testing of placebo patient samples for PK and ADA. The bioanalytical laboratory can be regarded as totally independent from the trial team. After the last patient completes the Week 12 visit the random plan will be released to the bioinformatics group. The bioinformatics group will receive the randomisation code in order to start with the pre-processing of gene expression data (using limma packages).

Bioinformatics groups and the analytical laboratory will not disclose the randomization code until the trial is officially unblinded.

A fully external DMC will perform an un-blinded safety and efficacy assessment at specified intervals in order to ensure that patients are protected from potential harm, please refer to [Section 7.4](#) for further details.

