### **Week 12 Primary Analysis**

The primary analysis of the trial will be performed once all randomised patients have completed the first 12 weeks of the trial, and a preliminary database lock will be done. Details of the analysis to be performed will be described in the TSAP which is planned to be finalized prior to achieving database lock for this primary analysis. Treatment will be unblinded at this time.

For further details regarding the maintenance and protection of the blind through the continuing trial subsequent to performance of the primary analysis, refer to [Section 4.1.5.1](#).

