#### **7.3.1 Primary endpoint analyses**

##### **Primary analysis**

The analysis of the gene expression values will be based on the RSS and will be conducted for biopsy location inner orifice and curettage. The analyses will be done by 'actual treatment'.

All analyses will be performed using the raw read counts for gene expression. This gene expression analysis is conducted for biopsy.

The RNA expression analysis will initially include all genes and all determined read counts. This means, if no gene expression values have to be excluded due to technical or other reasons, there is one read count value per person, per gene and per time point.

To get interpretable results several pre-processing steps are needed to correct e.g. for different sequencing depth. The following steps are conducted:

- Lowly expressed genes are filtered:
  - Genes for which at least 5 samples display a  $\text{cpm} \geq 1$  are used in the subsequent analyses.
  - normalization factors to scale the samples based on the raw library sizes are calculated using the weighted trimmed mean of M-values (TMM) method using the default parameters of edgeR's `calcNormFactors` function ([R18-2554](#)).

After these pre-processing steps the  $\log_2$  counts per million along with associated weights for each observation are then calculated based on the normalized library sizes from the previous step using limma's `voom` function [[R15-5383](#)]. Correlations between paired measurements per patient are estimated by the `duplicateCorrelation` function. For each gene, a repeated measures linear regression model will be utilized with treatment (BI 655130 or Placebo), visit (baseline, week 4), treatment by visit interaction as fixed effect and patient as a blocking factor. Hereby the weights for each observation are taken into account (13). This will be implemented using the `lmFit` function of the limma package.

Estimates for the mean  $\log_2$  fold change ratio for BI 655130 vs. Placebo at Week 4 will be calculated as

$$\log_2 \text{FC}_{\text{BIvsPBO}} = (\log_2 \text{BI}_{\text{Week 4}} - \log_2 \text{BI}_{\text{BL}}) - (\log_2 \text{PBO}_{\text{Week 4}} - \log_2 \text{PBO}_{\text{BL}}),$$

where baseline is the measurement at Visit V1c.

Changes will be quantified by  $\log_2$  fold changes (FC) and associated FDR adjusted p-values. Genes will be considered deregulated if they fulfil the following criteria:

- FDR adjusted p-value  $\leq 0.05$

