#### 7.4 INTERIM ANALYSES

The primary analysis of the efficacy and safety data collected up to week 12 will be performed once all randomised patients have completed the first 12 weeks of the treatment period (through visit 6). At that time point, a preliminary database lock will be done. Since the patients will be treated for another 12 weeks, the patients and the investigators (as well as the research staff at the trial site) must remain blinded. A logistics plan will be developed in order to describe the processes to be implemented for protecting the blinding (with regards to the patients and the investigators) and the integrity of the ongoing trial until the final database lock. Details of the analyses to be performed for the primary analysis, as well as for the final analysis after trial completion (through 36 weeks), will be described in the trial statistical analysis plan. Both the TSAP and the logistics plan will be finalized prior to the preliminary database lock for the primary analysis.

The primary analysis and final analysis may be performed as a single analysis (at the time of trial completion), if, prior to the time of the primary analysis, the trial team agrees that the expected time interval between the planned analyses is insufficient to justify the performance of separate analyses.

Further, a fully external DMC will be in place in order to ensure that patients are protected from potential harm, specific tasks are described in [Section 8.7](#).

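### The bioinformatics group may receive the randomisation code before the preliminary lock, and the visible text does not require RNA sample and value exclusions to be settled blind first (minor, cheap to improve)

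*Protocol*

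**What the plan says.** Protocol 4.1.5.1 (Blinding) states that the code "will not be accessible prior to the preliminary database lock for the interim analysis by anyone else involved in the trial with two exceptions". One exception is the bioanalytical laboratory, which is described as wholly independent of the trial team. The other is the bioinformatics group, for which no such statement is made. Its trigger is: "After the last patient completes the Week 12 visit the random plan will be released to the bioinformatics group". The purpose is given as: "The bioinformatics group will receive the randomisation code in order to start with the pre-processing of gene expression data (using limma packages"). The safeguard is: "Bioinformatics groups and the analytical laboratory will not disclose the randomization code until the trial is officially unblinded".

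The statistical plan has a different milestone. Protocol 7.3 says that it "which is planned to be finalized prior to achieving database lock for this primary analysis", and Protocol 7.4 says: "Both the TSAP and the logistics plan will be finalized prior to the preliminary database lock for the primary analysis".

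On which data enter the primary analysis, Protocol 7.3.1 starts from everything: "The RNA expression analysis will initially include all genes and all determined read counts". It then allows for a departure, since one count per person, gene and time point is expected only "if no gene expression values have to be excluded due to technical or other reasons". SAP 6.6.6 and 7.4 apply the as-observed approach, without visit windows or imputation. Membership of the RNA sequencing set (Protocol 7.3, SAP 6.3) requires a valid baseline and at least one valid post-baseline observation.

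**The concern.** The group that handles the primary-endpoint data may know each patient's treatment while it is still open which RNA samples or values count. A promise not to disclose protects everyone else's blind. It does nothing for decisions taken inside the group that holds the code.

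The primary endpoint is a count of genes passing an FDR and a fold-change threshold, from few patients: Protocol 3.3 plans about 20 randomised and lets screening stay open until about 15 have valid paired biopsies. If a sample were left out after release, a reader could not rule out that knowledge of treatment had influenced the list. Protocol 7.2 rules out confirmatory testing, so the stake is how far the count can be believed, not an error rate.

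**Working it through.** The plan gives no figure to reproduce; Protocol 7.7 states that the sample size does not come from a power calculation. The check is therefore mainly a comparison of passages.

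**1. Order of milestones.**
- Release to bioinformatics: after the last Week 12 visit, with no further condition (Protocol 4.1.5.1).
- Final statistical plan and logistics plan: before the preliminary lock (Protocol 7.4).
- Fixing of RNA sample and value exclusions: no milestone in the visible text.

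Because bioinformatics is an exception to the rule of no access before the lock, release may precede the lock. No actual release date is given.

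**2. Does the stated purpose need the code?** Protocol 7.3.1 lists two pre-processing steps.
- The low-expression filter keeps genes with cpm ≥ 1 in at least 5 samples. It uses counts only.
- TMM normalisation uses library sizes and default settings. It has no treatment term.

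The voom step and the linear model come after these. The model has treatment as a fixed effect and so needs the code. If the reference to limma in 4.1.5.1 means that modelling, the sample list, filter and normalisation can still be finished first.

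**3. What is open at release?**
- Fixed in Protocol 7.3.1: filter, normalisation, model, contrast, baseline visit (V1c), FDR ≤ 0.05, |fold change| ≥ 1.5.
- Open in the visible text: which values are dropped under the exception in 7.3.1, and which observations count as valid for the RNA sequencing set. Neither document says who decides or when.

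**4. How long is the window?** Visit 6 is Day 85 and the second biopsy visit (Visit 4) is Day 29. The gap is 85 − 29 = 56 days, so all tissue has been collected before release and sampling itself cannot be affected. Protocol 4.1.5.1 places the preliminary lock at the same Week 12 milestone, so the window may be short. If the primary and final analyses are merged, as Protocol 7.4 permits, the lock moves to after Visit 10 (Day 253): 253 − 85 = 168 days on planned visit days.

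**5. Size.** The documents supply no input for one. A simulation of the 7.3.1 contrast can serve only as an illustration. Its assumptions, none from the documents:
- 12,000 genes, 1,000 of them with |log2 fold change| = 1;
- within-patient correlation 0.4, taken as known; prior variance 0.5 or 0.8; 0 to 50% of variance from shared factors; voom weights omitted;
- three borderline patients, and an analyst who sees the count and then keeps everyone or leaves out one of the three.

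The ratio of the most favourable mean count to the all-patient mean ran from 131.7/131.7 = 1.00 to 37.3/28.7 = 1.30 with 8 vs 7 patients. With 10 vs 10 it ran from 309.0/309.0 = 1.00 to 89.9/86.0 = 1.05. Selection is deliberate and every input is assumed, so these ratios are not an estimate for this trial and the conclusion does not rest on them.

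**The case against.** The strongest reply is that most of the apparent freedom is already closed.

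- A reader might infer that the statistical plan could be finished with treatment known. The documents do not support this. Under Protocol 4.1.5.1 the code stays closed to others on the trial team until the lock, bioinformatics may not disclose it, and no passage gives that group a part in writing the plan. An initial version dates from January 2019 (SAP 10), and SAP 7.4 mostly refers back to Protocol 7.3.1.
- A reader might infer the same about protocol deviations, which can remove patients from the RNA sequencing set (SAP 7). SAP 6.2 gives those decisions to trial meetings, and under the same rule these stay blind until the lock whether or not bioinformatics holds the code.
- The default is to keep every read count, and release and lock share a milestone unless the analyses are merged. SAP 3 keeps a separate Week 12 lock.
- The missing rule may exist out of sight. Text after the primary analysis is redacted in both documents, most of Protocol 5.4 is redacted, SAP 5.4 and Section 9 are cited but not shown, and the logistics plan and site file are not available.
- Rerunning with every sequenced sample could put failed libraries back into the normalisation, so a changed result might reflect poor data rather than selection.

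All of this stands, and it narrows the point to RNA sample and value exclusions. It does not remove it: the release trigger is visible, carries no condition on those exclusions, and serves a purpose whose listed steps do not need the code.

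**Conclusion.** The point holds as a minor improvement to the release condition in Protocol 4.1.5.1. The visible text lets the group handling the primary-endpoint data hold the code before RNA sample and value exclusions are settled, with non-disclosure as its only safeguard.

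It would go too far to conclude that the gene count is biased, that the final plan of February 2022 followed the release, or that an error rate is inflated. No release date is given, no passage shows treatment knowledge being used, and no confirmatory test exists whose error rate could suffer. No size can be drawn from the documents.

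The conclusion assumes that redacted or unavailable text does not already require a blind sample list. If it does, the point reduces to a cross-reference.

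**What to change.** In Protocol 4.1.5.1, and repeated in the logistics plan, release the code to bioinformatics only after a dated, signed list of included and excluded RNA samples and values, with reasons, has been fixed blind to treatment. The list should cover membership of the RNA sequencing set by sample validity. Run the expression filter and TMM normalisation before release. The condition belongs in 4.1.5.1 itself, because the logistics plan is due only before the lock and could come after the release.

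If a sample that yielded read counts is excluded for a reason other than a documented technical failure, or is excluded after release, report one sensitivity run that includes it. This limit keeps failed libraries out of the rerun. If the code is already out, report the release date and the date on which the list was fixed.

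The cost is one signed file, possibly one extra run, and perhaps a short delay before modelling. Biopsy validity may already have to be judged during recruitment, given the target of about 15 patients in Protocol 3.3, so the list should add little work.

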#### 4.1.5.2 Unblinding and breaking the code

##### Study Cohort, Period 1 and 2:

Emergency unblinding will be available to the investigator / pharmacist / investigational drug storage manager via IRT. It must only be used in an emergency situation when the identity of the trial drug must be known to the investigator in order to provide appropriate medical treatment or otherwise assure safety of trial participants. The reason for unblinding must be documented in the source documents and/or appropriate CRF page along with the date and the initials of the person who broke the code.

Due to the requirements to report Suspected Unexpected Serious Adverse Reactions (SUSARs), it may be necessary for a representative from BI's Pharmacovigilance group to access the randomisation code for individual patients during trial conduct. The access to the code will only be given to authorised Pharmacovigilance representatives and not be shared further.

Treatment unblinding will be performed prior to each DMC meeting as a prerequisite for generation of the applicable DMC summaries required.

#### 4.1.6 Packaging, labelling, and re-supply

The investigational products will be provided by BI or a designated CRO. They will be packaged and labelled in accordance with the principles of Good Manufacturing Practice (GMP). Re-supply to the sites will be managed via an IRT system, which will also monitor expiry dates of supplies available at the sites.

For details of packaging and the description of the label, refer to the ISF.

#### 4.1.7 Storage conditions

Drug supplies will be kept in their original packaging and in a secure limited access storage area according to the recommended storage conditions on the medication label. A temperature log must be maintained for documentation.

If the storage conditions are found to be outside the specified range, the local clinical monitor (as provided in the list of contacts) must be contacted immediately. Refer to ISF.

Trial medication must be securely stored, e.g. in a locked refrigerator or at a pharmacy. The medication may only be dispensed to trial patients according to the Clinical Trial Protocol (CTP) by authorized personnel as documented in the trial staff list.

IMP will only be prepared for infusion just prior to the administration.

#### 4.1.8 Drug accountability

The investigator/pharmacist /investigational drug storage manager will receive the investigational drugs delivered by the sponsor when the following requirements are fulfilled:

- Approval of the clinical trial protocol by the IRB / ethics committee ,
- Availability of a signed and dated clinical trial contract between the sponsor and the investigational site,
- Approval/notification of the regulatory authority, e.g. competent authority,
- Availability of the curriculum vitae of the Principal Investigator,
- Availability of a signed and dated clinical trial protocol,
- Availability of the proof of a medical license for the Principal Investigator,
- Availability of FDA Form 1572 (if applicable).

Investigational drugs are not allowed to be used outside the context of this protocol. They must not be forwarded to other investigators or clinics.

The investigator/pharmacist/ investigational drug storage manager must maintain records of the product's delivery to the trial site, the inventory at the site, the use by each patient, and the return to the sponsor or warehouse / drug distribution centre or alternative disposal of unused products. If applicable, the sponsor or warehouse / drug distribution centre will maintain records of the disposal.

These records will include dates, quantities, batch / serial numbers, expiry ('use- by') dates, and the unique code numbers assigned to the investigational product and trial patients. The investigator / pharmacist / investigational drug storage manager will maintain records that document adequately that the patients were provided the doses specified by the CTP and reconcile all investigational products received from the sponsor. At the time of return to the sponsor or appointed CRO, the investigator / pharmacist / investigational drug storage manager must verify that all unused drug supplies have been returned by the clinical trial patient and that no remaining supplies are in the investigator's possession

## 4.2 OTHER TREATMENTS, EMERGENCY PROCEDURES, RESTRICTIONS

### 4.2.1 Other treatments and emergency procedures

Section 4.2.1 is applicable for the *Study Cohort* and not for the *Screening Cohort*.

Patients in this trial may be on conventional **immunosuppressants** or anti-TNF $\alpha$  biologic treatment for CD. **These** may consist of one or more of the following drugs (cf. [Section 4.2.2.1](#) for restrictions), which are therefore permitted concomitant medications:

- Oral 5-ASA compounds, provided that dose has been stable for  $\geq 2$  weeks prior to randomisation, and/or
- Oral corticosteroids ( $\leq 20$  mg per day of prednisone or equivalent), provided that dose has been stable for  $\geq 2$  weeks prior to randomisation, and/or
- Oral budesonide ( $\leq 9$  mg per day), provided that dose has been stable for  $\geq 2$  weeks prior to randomisation, and/or
- Azathioprine, 6-MP, 6-TG or methotrexate, provided that dose has been stable for  $\geq 8$  weeks prior to randomisation
- Approved anti-TNF $\alpha$  (e.g. infliximab, adalimumab, certolizumab pegol; or respective biosimilars) provided that
  - i. dose has been stable for at least 6 months prior to screening and
  - ii. Rest of eligibility criteria are met ( i.e activity of the fistula based on clinical and MRI assessment at screening, [see inclusion criterion 4](#)).
- Probiotics (e.g. *S. boulardii*) provided that dose has been stable for  $\geq 4$  weeks prior to randomisation
- Regular use of anti-diarrheals

Dose has to be stable throughout the trial. The only exceptions are anti-diarrheals, which may be adjusted to current symptoms, and steroid *reduction*, which is allowed after week 12 to a minimum dose of 10 mg/d (budesonide: 6 mg/d) according to local standard of care.

